10.4. Safety (DCD Heart Transplanted Recipient Population Only)

Serious Adverse Events (SAEs) and Heart Graft-related Serious Adverse Events (HGRSAEs) will be collected within the first 30 days post-transplant and the mean number of HGRSAEs per subject will be summarized using descriptive statistics. HGRSAEs are defined as the following adverse events (at most one per type): Moderate or Severe heart PGD (left or right ventricle) (not including rejection or cardiac tamponade) according to ISHLT consensus manuscript (as defined in [Appendix 1](#)) and primary graft failure requiring retransplantation.

SAEs and HGRSAEs will also be tabulated using counts and percentages alone and in regards to the relationship of the HGRSAE to the device, and the severity of the HGRSAE.

10.5. Sample Size Determination

We have assumed that transplantation of a DCD donor heart will occur at the same ratio as SOC heart transplants, despite the 3:1 randomization of ***DCD Heart Possible*** to ***SOC Heart Only***. The sample size calculations are based on the following specifications:

- Non-inferiority study with comparison of DCD heart transplanted recipients to SOC heart transplanted recipients
- Primary endpoint is patient survival at 6 months post-transplant
- One-sided normal approximation test

- Alpha = 0.05
- Power = 80%
- Assume 1:1 occurrence of SOC heart transplants (SOC1 and SOC2) and DCD heart transplants
- True SOC survival percentage = 93%
- True DCD survival percentage = 85%
- Non-inferiority margin = 20%.

Based on these assumptions, a sample size of 84 DCD heart transplanted recipients and at least 84 SOC heart transplanted recipients will provide at least 80% power.

This sample size was increased to 90 per group to reflect subjects who are lost to follow-up, withdraw or do not meet eligibility criteria.

To ensure timely completion of the trial, TransMedics proposes the following modification to the enrollment of SOC subjects:

1. As soon as 90 DCD recipients are transplanted, the trial enrollment will stop, regardless of the number of SOC transplanted recipients.
2. If, at the time the 90th DCD recipient is transplanted, the SOC enrollment is less than the proposed 90 subjects, the outcomes for the remaining subjects will be obtained from the UNOS registry by accessing patient and graft demographics and survival data for SOC subjects transplanted at the participating Heart DCD trial investigational sites over the previous 2 years. The distribution of SOC subjects obtained from UNOS will reflect the distribution of enrollment in the Heart DCD among the various sites.
3. The final SOC1 and SOC2 patient cohorts will include the subjects transplanted in the trial, supplemented with subjects obtained from UNOS at the same investigational sites, to reach the SOC sample size of 90 subjects.

11. RISK ANALYSIS

This clinical trial has been designed to ensure that the benefits and knowledge gained from the trial outweigh the potential risks to the subjects.

11.1. Potential Risks

The potential risks to subjects from participation in this clinical trial include the following:

- **Potential Risks Associated with Heart Transplant Procedures:** These risks include post-operative complications not associated with the OCS Heart System such as graft failure, primary graft dysfunction, rejection, infection and other organs/systems complications, graft vessel disease (an expression of chronic rejection), abnormal kidney function, diabetes, high level of cholesterol, high blood pressure, cancer and neurological complications.

- **The Potential Risks Associated with OCS Heart System:** Subjects have the risk of not receiving organs preserved with the OCS Heart System under certain conditions including: (1) the OCS Heart System may not work properly, or there may not be personnel available trained in the use of the Heart System or (2) the OCS Heart System may malfunction, or the medical staff may make an error which could lead to damage of the donor heart. If this occurs, the subject will have to wait for a new donor heart to become available. As with any medical device, there is always a risk of extremely rare or previously unknown side effects developing from the treatment.
- **Potential Risk of Using a Donor Heart that is Unsuitable for Transplantation:** Regardless of the preservation system that is used, there is the risk that a patient can receive a heart that does not adequately function. This trial is designed to utilize hearts that would not be accepted for transplantation using cold storage preservation. There is the possibility that using such hearts may increase the risk of transplanting a heart that does not function appropriately. It is also possible that the donor heart may not meet transplantability criteria after OCS preservation and would be turned down for transplant. In the EXPAND trial and in trials of DCD donors conducted outside the U.S., only 20% of the donor hearts were turned down following OCS preservation so the anticipated frequency of this event is low.

11.2. Manner in Which the Potential Risks Have Been Minimized

The Sponsor has relied upon a number of different means, including the device design, risk analysis and management process, preclinical testing, and the clinical protocol itself, to minimize the risks to subjects and to protect their safety and welfare.

The OCS has undergone extensive preclinical and animal studies to demonstrate that the device performs as intended and all materials are biocompatible. Previous clinical studies, including the Heart EXPAND trial and studies of DCD hearts performed outside the U.S., have not indicated any safety signals that would preclude initiation of this study.

In addition, this clinical protocol incorporates several procedures to minimize the risks to subjects and to ensure the benefits of the clinical trial outweigh its potential risks.

- The donor heart acceptance criteria after OCS Heart perfusion and assessment are based on clinically relevant markers for perfusion of donor hearts on OCS and clinical standards of accepting conventional donor hearts for transplantation. Thus, the donor heart will be fully assessed based on the current standards of evaluating donor hearts before accepted for transplantation. The recipient should not be subjected to any surgical or medical procedures until the heart has been accepted for transplantation by the transplanting team.
- As with any heart transplant procedure, subjects will be monitored before, during and after the operative procedure. The investigators have extensive experience with heart transplants and will be trained to use the OCS Heart System to further minimize risk.
- The trial will be monitored to ensure the identification, documentation, and analysis of adverse events; and to ensure compliance with the protocol and procedures that are in place for conducting research to protect the safety and well-being of all subjects.

11.3. Potential Benefits

The low utilization of donor hearts has led to a severe shortage of donor hearts to meet the large and growing need for heart transplantation; the Scientific Registry for Transplant Recipients (SRTR) and Organ Procurement Transplant Network (OPTN) report that approximately 25% of the patients on the national waiting list have either died or their health deteriorated prior to a heart transplant procedure.

The OCS Heart System's preservation and assessment capabilities could potentially increase the rate of utilization of donor hearts that are not used due to the limitations of cold storage techniques. The previous Heart EXPAND study demonstrated an 80% utilization of these expanded criteria donor hearts, and studies of the OCS performed outside the U.S. observed 78 - 80% utilization of DCD hearts. This could improve the chances of waiting list recipients to receive a lifesaving heart transplant and reduce waiting list time and mortality. In addition, the OCS heart's ability to assess donor hearts after removal allows for the assessment the function of the donor heart before it is transplanted.

11.4. Risks Benefit Ratio

Based on the above, the benefits of using OCS Heart technology to recruit, preserve and assess donor hearts to ensure their suitability for heart transplantation outweigh the potential risks to trial subjects.

12. DEVICE/SITE MANAGEMENT

12.1. Packaging and Labeling

The OCS Heart Perfusion Set and accessories and the Perfusion Solution will be supplied sterile and are intended and labeled for single use only.

The OCS and its components will be clearly labeled as an investigational device according to 21 CFR 812.5. The labeling provides instructions for use for the device. A copy of the Instructions for Use will be provided to each investigational site.

12.2. Storage

The investigational devices will be stored in a secure location. Access should be strictly limited to the investigators and their designees. Neither the investigators nor any designees may provide the investigational device to any subject not participating in this trial. The OCS Heart Perfusion Set should be stored at temperatures between -20°C and 50°C, and ambient humidity from 10-95%, no condensing.

Note: The OCS Heart Perfusion Set should be operated at ambient temperatures (10°C to 35°C), and ambient humidity (20%-90%).

12.3. Accountability

The investigator or designee will maintain a record of investigational devices received, used, discarded, or returned to the Sponsor.

12.4. Device Complaints and Malfunctions

The investigator will inform the Sponsor of any complaints or malfunctions during the course of the trial. The Sponsor will investigate all device complaints and malfunctions.

13. REGULATORY/ETHICS

This clinical trial will be conducted in accordance with the requirements of the FDA Investigational Device Exemptions regulation (21 CFR Part 812), ISO Standard 14155, and in accordance with good clinical practices.

13.1. Institutional Review Boards (IRB)

Prior to initiation of any trial procedures, trial documents will be submitted to each site's IRB for review and approval. In addition, any amendments to the protocol or informed consent form will be reviewed and approved (if necessary) by the IRB. The Sponsor must receive a letter documenting the IRB's or EC's approval at the clinical site prior to the initiation of the trial at that particular site.

13.2. Informed Consent

The IRB approved written informed consent form will be signed and dated by the subject and the individual obtaining the consent. The subject will be given a copy of the signed informed consent form. The original will be kept in the patient's file by the investigator.

A copy of the proposed draft Informed Consent template is included in [Appendix 3](#).

14. DATA COLLECTION/RECORDS/REPORTS

14.1. Investigator Records

Prior to participation in the investigation, the investigators will provide the following documentation to the Sponsor:

- Signed Investigator Agreement
- Signed financial disclosure form
- Curriculum Vitae (CV).

Written approval of the protocol and informed consent document from the IRB; Investigators will be responsible to maintain on file the following records (Note that this is not the complete list of items to be maintained):

- All relevant correspondences and required reports that pertain to the trial
- Records of receipt, use or disposition of the investigational device
- Records of each subject's case history and exposure to the device
- Signed and dated consent forms
- Relevant observations, including records concerning adverse events, condition of each subject upon entering and results of diagnostic tests

- Protocol, and any amendments
- Subject recruiting materials
- Investigator curricula vitae.

The investigator will not dispose of any records relevant to this trial without: (1) written permission from the Sponsor and (2) providing an opportunity for the Sponsor to collect such records. The investigator will take responsibility for maintaining adequate and accurate electronic or hard copy source documents of all observations and data generated during this trial. Such documentation is subject to inspection by the Sponsor and regulatory authorities.

14.2. Investigator Reports

In accordance with the FDA reporting requirements, the investigators will be required to prepare and submit to the Sponsor the following complete, accurate, and timely reports on this investigation when necessary:

- The investigator will notify the Sponsor of a subject death occurring during the investigation as soon as possible, preferably within 24 hours of learning of the subject's death, but in no event later than 48 hours. The investigator will also notify the Sponsor immediately of a serious adverse event, preferably within 48 hours of learning of the serious adverse event, but in no event later than 5 working days.
- The investigator will notify the Sponsor of any unanticipated adverse device effects (UADE) preferably within 48 hours after the investigator first learns of the effect, but in no event later than 5 working days. The investigator will notify its IRB of any unanticipated adverse device effects as soon as possible, but no later than 10 working days after the investigator first learns of the effect.
- The investigator will notify the Sponsor of the withdrawal of IRB approval as soon as possible, but no later than 5 working days after the investigator first learns of the withdrawal
- The investigator will provide current progress reports to the Sponsor and reviewing IRB at regular intervals but at least on an annual basis.
- The investigator will notify the Sponsor and the IRB of any deviation from the investigational plan to protect the life and physical well-being of a subject in an emergency as soon as possible, but no later than 5 working days after the emergency occurred.
- The investigator will notify the Sponsor and IRB that an informed consent was not obtained from a subject as soon as possible, but no later than 5 working days after such an occurrence.
- The investigator will provide a final summary report within 3 months after termination or completion of the trial to the IRB. The site trial completion report may serve as the trial completion for the Sponsor.
- The investigator will provide any other information upon the request of the IRB, or the Sponsor.

14.3. Data Collection

All data required by the trial protocol will be entered into the trial database by the investigator or his or her designate. A copy of draft eCRFs is provided in [Appendix 4](#).

14.4. Source Documents

Original documentation supporting the data recorded on the CRFs must be maintained, and may include clinical charts, medical records, laboratory reports, physician referral or consultation letters, x-ray reports, etc. Adverse events which are managed at a health care facility other than the study site must be reported on the case report form and every attempt must be made to obtain source documentation from that facility.

During monitoring visits, source documents will be reviewed to ensure accuracy and validity of data recorded on the CRFs. Source document verification will be performed by TransMedics or its designee, with due regard to subject confidentiality.

14.5. Archiving of Records

Essential trial documents must be maintained by the Investigator for at least 2 years after the last marketing approval by a regulatory body, as determined by the Sponsor. The documents should be retained for a longer period, however, if required by the applicable regulatory requirements. Records will be kept in a secure, dry location controlled by the institution.

15. CLINICAL MONITORING

15.1. Monitoring

The trial will be monitored by TransMedics. All monitors will be qualified by education, training, and experience. After the study has been initiated, TransMedics or its designee will perform periodic monitoring visits to assess study progress, perform device accountability, assess the adequacy of records, and to ensure adherence to the study protocol. Monitoring visits could be done live or via webconference.

A summary of the monitoring visit, including documentation of completed previous action items and/or new or outstanding action items, and/or significant findings will be provided to the Investigator.

In addition to periodic monitoring visits, TransMedics may perform remote monitoring to ensure data are submitted in a timely manner. Ongoing communication with investigators and study staff will be performed through written correspondence and telephone conversations.

Details related to site monitoring will be documented in the Sponsor's study-specific monitoring plan.

If the investigator is not complying with the signed Investigator Agreement, the protocol, or any condition of the trial, (e.g., incomplete data forms) the Sponsor has the right to terminate the investigator's participation in the trial. The Sponsor's general monitoring procedures for investigational studies are described below.

15.2. Site Initiation Visit

TransMedics or its designee will be responsible for determining and documenting that each investigator clearly understands and accepts the responsibilities and obligations incurred in conducting a clinical study. The sponsor or its designee will ensure, prior to study initiation, that the investigator:

- Understands the requirements for device accountability
- Understands the requirements of the clinical protocol
- Understands reporting obligations
- Understands and accepts the obligations to obtain informed consent
- Understands and accepts the obligation to obtain Institutional Review Board approval of the protocol and informed consent form prior to the enrollment of the first subject.
- Has adequate facilities to conduct the investigation.

Site initiation could be done via webconference.

15.3. Periodic Monitoring Visits

Monitoring visits will be conducted as scheduled by the sponsor. The monitor should visit (or conduct the visit via webconference) with each site as needed to ensure the following:

- Facilities continue to be adequate and acceptable.
- Informed consent has been obtained.
- The protocol is being properly followed.
- The IRB has approved or been notified of any protocol changes.
- Accurate, complete and current records are being maintained, and the information recorded and submitted to the Sponsor is representative of the subject's record and other supporting documentation.
- Accurate, complete and timely adverse event reports are being submitted to the Sponsor.
- The reason for a subject's withdrawal from the trial has been documented.
- Reports are being submitted to the IRB and Sponsor.
- The appropriate staff is carrying out trial activities.

15.4. Frequency of Monitoring Visits

The frequency of monitoring visits will be determined on the basis of several factors, including the duration of the trial, number of subjects enrolled, number of investigators/sites, complexity of the trial, and number of outstanding issues from previous visits.

15.5. Study Close-out Visit

The study close-out visit may be combined with a monitoring visit. The following tasks will be completed at close-out visit.

- Ensure that all required CRFs have been completed/submitted.
- Ensure final disposition of investigational devices.
- Remind the investigator of the obligation to retain the records in accordance with local country requirements, and prepare a final report for the sponsor and Institutional Review Board.

15.6. Protocol Deviations

The study should be conducted as described in this protocol. All deviations from the protocol should be reported to the Sponsor by entering a protocol deviation form into the study database.

For sites who demonstrate repeated deviations that may affect the safety of subjects, and/or the integrity of the data, corrective measures will be instituted such as re-training. Continued protocol deviations may result in the site's termination from the trial.

15.7. Clinical Events Committee (CEC)

The Sponsor will utilize an independent Clinical Events Committee (CEC) to provide individual serious adverse event adjudication for the trial. It is anticipated that the CEC will meet with the Sponsor on a periodic basis, or as needed, depending on the rate of patient accrual. The CEC will be guided by the CEC Charter; however, the primary responsibilities of the CEC are to:

- Review reportable serious adverse events, including PGD, that occur over the course of the trial and the subsequent classification of these adverse events as related to the device.
- Provide recommendations to extend the length of follow-up past 30 days post-transplant for a subject experiencing a serious adverse event.

15.8. Data Safety Monitoring Board & Stopping Rules

An independent Data Safety Monitoring Board (DSMB) will be established by the Sponsor to periodically assess the progress of the trial, the safety data and the primary efficacy and safety endpoints. The DSMB will make recommendations to the Sponsor regarding continuation, modification or termination of the clinical trial. The DSMB will review all data submitted to them by the Sponsor and may request additional information to assist in their decision process. They will attend scheduled meetings and issue written minutes of their meetings; furthermore, the appointed Chair will be responsible for issuing final written recommendations.

The following stopping rule is to be used in the study:

- Stopping Rule: Let p denote the true proportion of recipients transplanted with an OCS-treated heart for whom the recipient does not survive until Day 30. Whenever a recipient dies within 30 days post-transplant, calculate a 97.5% lower confidence bound for p . Stop the study if this lower confidence bound exceeds 0.15 (15%).

Table 3 below shows the conditions under which the study would be stopped for a range of number of deaths (m) and a range of number of recipients (n). (The above stopping rule would, however, be applied to all combinations of number of deaths and number of recipients that were observed in the study.) The word "Stop" in a cell indicates that the study would be stopped if this condition were met. If the word "Continue" appears, the study would continue. A dash indicates an impossible condition, with $m > n$. One sees, for example, that the study would be stopped if there were 4 deaths out of the first 5 recipients or 5 deaths out of the first 10 recipients.

Table 3: Conditions under which Study Would be Stopped

n	M											
	1	2	3	4	5	6	7	8	9	10	11	12
5	Continue	Continue	Continue	Stop	Stop	-	-	-	-	-	-	-
10	Continue	Continue	Continue	Continue	Stop	Stop	Stop	Stop	Stop	Stop	-	-
20	Continue	Continue	Continue	Continue	Continue	Continue	Stop	Stop	Stop	Stop	Stop	Stop
30	Continue	Stop	Stop	Stop								
40	Continue	Stop										

TransMedics will be responsible for implementing the stopping rule.

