- The incidence of ISHLT severe PGD was 10.7%, and the incidence of ISHLT moderate or severe PGD was 14.7%. These rates compare favorably with contemporary literature reporting PGD rates post-heart transplantation using the ISHLT criteria.
- Survival at 30 days, 6 months, and 12 months was 95%, 88%, and 84%, respectively.
- The FDA also approved a Continued Access Protocol (CAP) for EXPAND called the EXPAND CAP. The study is on-going and data are still being collected, but based on the available data the results show:
 - 38 donor hearts were preserved and assessed on the OCS Heart System.
 - The utilization rate is 89.5%, with 34 of 38 extended criteria donor hearts successfully transplanted.
 - The first 20 transplanted patients have reached a minimum of 30-day follow-up and all survived (100% survival at 30-days).
 - No severe LV or RV ISHLT PGD has been reported among the first 20 subjects transplanted.
- PROCEED II was the first pivotal study of the OCS Heart System. It was a randomized study of the OCS Heart System compared to standard of care cold storage, and it enrolled standard criteria donor hearts. The study met its primary endpoint and non-inferiority was shown in 30-day survival, as well as in the secondary endpoint, i.e., cardiac graft-related SAEs. Longer-term data, obtained from the SRTR database, showed lower survival rates for the OCS group at 2-3 years of follow-up; however, the incidence of cardiac graft-related deaths was similar and other deaths were typical for heart transplant recipients (late infection, malignancy, multi-organ failure). The results of this study were published in the Lancet (Ardehali, et al., 2015).
- Studies of the OCS Heart System for preservation of standard criteria donor hearts conducted outside the U.S. at hospitals in Germany and the UK showed improved rates of survival and lower rates of PGD for OCS compared to standard of care cold storage (Koerner, et al., 2014).

2.5. Overall Summary of Clinical Data to Support Initiation of OCS Heart DCD Trial

In summary, studies of the OCS Heart System for the preservation of DCD hearts have been performed outside of the U.S. These studies have shown 77.8 - 86.7% utilization rate, with 90-day and 1-year survival comparable to outcomes obtained with standard criteria donor hearts preserved using cold storage standard of care.

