8.3. Long-term Follow-up: 6 and 12 months

Follow-up data collection will be conducted at 6 months (\pm 30 days) and 12 months (\pm 60 days) post-transplant to evaluate patient survival, graft survival and diagnosis of cardiac allograft vasculopathy. These follow-ups may be performed by phone.

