8.4.5. Reporting of Adverse Events

Unanticipated adverse device effects (UADE) should be reported to TransMedics, Inc., within 48 hours of the time the investigator learns of the event, but in no case later than 5 working days after learning of the event.

All SAE information will only be collected from transplant through day 30. SAEs should be entered into the study database as soon as possible. SAE will be followed until the investigator designates the event to be either resolved or its effect on the patient's condition stabilized. Details related to treatment of the SAE will also be collected.

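### Protocol 15.8's only numerical stopping rule ends at Day 30; DCD deaths from Day 31 to Month 6 have no numerical trigger and no stated time for reaching the DSMB

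*Protocol*

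**What the plan says.** Protocol 15.8 sets one stopping rule: "Whenever a recipient dies within 30 days post-transplant, calculate a 97.5% lower confidence bound for p". The study stops if that bound exceeds 0.15. SAP 5.4 plans no interim analyses, and neither document gives another numerical trigger.

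Beyond the rule, 15.8 asks an independent DSMB to "periodically assess the progress of the trial, the safety data and the primary efficacy and safety endpoints", so 6-month survival is within its remit. It may ask for more information and may recommend continuing, modifying or terminating the trial. On how it works: "The DSMB will review all data submitted to them by the Sponsor", and "They will attend scheduled meetings and issue written minutes of their meetings". No meeting frequency or ad hoc meeting is mentioned.

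On what is collected after Day 30, Protocol 8.4.5 says "All SAE information will only be collected from transplant through day 30". Protocol 8.3 places the next follow-up at 6 months, and "These follow-ups may be performed by phone". Protocol 14.2 is broader: "The investigator will notify the Sponsor of a subject death occurring during the investigation as soon as possible, preferably within 24 hours", with 48 hours as the outer limit and no Day 30 cut-off.

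A late death could also surface by other routes:
- follow-up of an SAE that began by Day 30 (8.2, 8.4.5);
- follow-up extended on the recommendation of the Clinical Events Committee (15.7);
- a UADE report (8.4.3, 14.2).

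**The concern.** The rule's horizon is 30 days and the endpoint's is 6 months. A DCD death at Day 45 counts fully against the primary endpoint and never enters the rule. The investigator must tell the sponsor quickly, but the protocol does not say when the sponsor must tell the DSMB, and nothing short of the next scheduled meeting prompts the board to look.

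If 6-month DCD mortality were unacceptable and much of it fell after the first month, the rule could stay silent while transplants continued. What is at stake is how many recipients are transplanted before the DSMB looks. The validity of the final test is not affected.

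**Working it through.** **Reproduce the rule.** The bound is the exact (Clopper-Pearson) one-sided 97.5% lower limit, the 0.025 quantile of Beta(m, n − m + 1). Results: 3/5 gives 0.147 and 4/5 gives 0.284; 4/10 gives 0.122 and 5/10 gives 0.187; 6/20 gives 0.119 and 7/20 gives 0.154. The first counts that stop are 4/5, 5/10, 7/20, 10/30, 12/40 and 21/90. These agree with Protocol Table 3 where it is legible. The rule is calculated correctly.

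**Mortality at the inferiority limit.** Protocol 10.5 assumes 93% SOC survival with a 20-point margin. So DCD survival is 93 − 20 = 73%, and mortality is 27%. Planned DCD mortality is 100 − 85 = 15%.

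**Share of 6-month deaths that fall by Day 30.** The documents do not give this for DCD hearts.
- The sponsor's extended-criteria trial (Protocol 2.4, not DCD) reports: "Survival at 30 days, 6 months, and 12 months was 95%, 88%, and 84%, respectively". The early share is (100 − 95)/(100 − 88) = 5/12. With 75 recipients that is about 4 of 9 deaths, exact 95% CI 0.137 to 0.788.
- The DCD series show no late-death pattern. One had 12 recipients and no deaths at 25 to 829 days (2.3.2). Another had 5 recipients and one death, within 30 days, in a retransplant patient whom this trial would exclude (2.3.3).
- The direct-procurement arm in 2.3.1 had 2 deaths among 14 by Day 90, not split at Day 30.

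These series are too small to settle the share, so it is varied below.

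**Written rule alone.** Exact recursion over n = 1 to 90, checked at each early death, with no reporting lag and no DSMB action. Total 6-month mortality is 27%:

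| Early share of deaths | 30-day mortality | P(stop) |
|---|---|---|
| 5/12 | 11.25% | 0.032 |
| 20/27 (20% early, 7% late) | 20% | 0.419 |
| 78% | 21% | 0.500 |
| 90% | 24.3% | 0.747 |
| 100% | 27% | 0.885 |

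**Gain from a death-driven trigger.** The fair comparator is the existing rule plus a DSMB that applies the same bound to all deaths at each meeting. Assumptions that are not in the documents:
- 90 transplants uniform over 6, 12, 18, 24 or 36 months;
- meetings every 3 or 6 months;
- early deaths uniform over months 0 to 1, late deaths uniform over months 1 to 6;
- all recipients transplanted to date in n.

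Probability of a review or stop before the 90th transplant at 27% mortality (40,000 simulated trials per setting), for accrual 6/12/18/24/36 months:

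| Early share | Rule + 3-monthly DSMB | Rule + 6-monthly DSMB | With trigger |
|---|---|---|---|
| 5/12 | .004/.195/.434/.565/.693 | .003/.044/.264/.444/.608 | .084/.471/.638/.713/.779 |
| 20/27 | .220/.451/.604/.684/.761 | .216/.333/.483/.591/.694 | .415/.684/.763/.797/.827 |
| 90% | .541/.672/.730/.765/.803 | .540/.650/.699/.733/.772 | .624/.771/.810/.830/.847 |

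Gains in percentage points:
- 5/12 share: 8/28/20/15/9 (3-monthly) or 8/43/37/27/17 (6-monthly).
- 20/27 share: 20/23/16/11/7 or 20/35/28/21/13.
- 90% share: 8/10/8/6/4 or 8/12/11/10/8.
- 100% share: zero.

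When the trigger fires before the 90th transplant, review comes earlier by these average numbers of transplants: 8.7 to 14.5 (3-monthly) or 13.9 to 21.8 (6-monthly) at 5/12; 7.0 to 11.6 or 11.0 to 16.1 at 20/27; 3.5 to 5.0 or 3.6 to 6.4 at 90%, where the median is 0.

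At 20% mortality, 5/12 share and 3-monthly meetings, a smaller run of 4,000 trials gives about 5 points at 12-month accrual and 7 at 24 months.

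**Unneeded reviews at the planned 15% mortality.**
- 5/12 share: 2.4% to 4.7%; the existing rule alone already stops 0.0% to 0.2%.
- 20/27 share: 2.6% to 6.7%; existing rule 0.3% to 1.8%.
- 90% share: 3.2% to 7.9%; existing rule 1.6% to 4.9%.

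Used instead as a binding stop on complete 6-month outcomes without lag, the 0.15 level would stop 11.5% of trials that perform exactly as planned.

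**The case against.** Limiting an automatic stop to 30-day death and leaving later mortality to the DSMB's judgement is an ordinary design choice. The board's remit covers the primary endpoint, it can ask for data, and the sponsor hears of any death within 48 hours. Meeting frequency and forwarding times may be set in a charter that is not among the documents. The benefit is shown at 27% mortality, and the least favourable early share comes from a non-DCD trial with about nine deaths. With monthly meetings at the 5/12 share, the gain falls to about 11 points at 12-month accrual and 5 at 24. Finally, SAP 3.2 and 3.5 show that enrolment is complete, so no transplant in this trial can now be deferred.

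Much of this stands and limits the weight of the point. It does not close the gap in the protocol as written: the sponsor-to-DSMB step has no stated time, and no count of late deaths prompts a review.

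A reader might infer three stronger things that the documents do not support:
- That late deaths go unreported or unmonitored. Protocol 14.2 and the DSMB remit in 15.8 say otherwise.
- That the 3% figure describes the trial's oversight. It describes the rule alone, at one assumed share, with the DSMB ignored.
- That DCD deaths tend to come late. The cited DCD series show no such pattern and are too small to exclude one.

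**Conclusion.** The point holds as a modest, inexpensive safety improvement, and the existing rule contains no error. The rule covers one month of a six-month mortality endpoint, and later DCD deaths depend on scheduled meetings of unstated frequency. The added chance of review before the 90th transplant runs from nil (all deaths early) to about 43 points (5/12 share, 12-month accrual, 6-monthly meetings). It rests on assumed accrual, meeting interval and early share, and is smaller in the 20% mortality settings given above. A DSMB that meets often, or whose charter already holds such a trigger, would gain less. With enrolment complete, the point bears on the plan as written and on any later protocol that reuses this section.

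**What to change.** Keep the 30-day rule and add two or three sentences to Protocol 15.8:

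1. At each DCD death through Month 6, compute the exact 97.5% lower bound on DCD deaths to date over DCD recipients transplanted to date. If it exceeds a level that the DSMB fixes before enrolment, the DSMB holds a prompt ad hoc review. A level of 0.15 is a workable default for calling a review. It should not be a binding stop, because it equals the planned 6-month DCD mortality.
2. State that this is an alert statistic. It is not a confidence bound on 6-month mortality, because recent recipients have incomplete follow-up, and its behaviour therefore depends on the speed of accrual.
3. The sponsor forwards every DCD death through Month 6 to the DSMB when it is notified.

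No new data, committee or SAP change is needed. The price is an unneeded ad hoc review in roughly 2% to 8% of trials at planned mortality, part of which the existing rule would already stop. The review may lead to continuation, modification, a pause or termination. It offers no early claim of non-inferiority.
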